8.2.5 Proportion of Seizure Free Subjects

Proportion of subjects who completed the DB portion of the study and did not experience any seizures during the maintenance period of the study, and proportion of subjects who experienced at least one 28-day seizure free period anytime during the DB phase of the study (titration + maintenance) will be calculated.

A frequency table will summarize the responses for each treatment in DB phase for Cohort 1 and Cohort 2. The proportions of seizure free subjects between treatment groups will be compared

using a Logistic Regression Model, with terms for treatment, pooled center (either US or ROW) and baseline number of seizure free days per 28-day period in the model. The numbers and percentage of seizure free subjects will be summarized descriptively. The test for treatment effect is a test of whether the coefficient of the treatment term is equal to zero. The odds ratio and its associated 95% confidence interval and p-value according to the Logistic Regression Model will be reported.

[figure not shown]
Summary table with descriptive statistics also will be provided in OL phase in both Cohort 1 and Cohort 2.

8.2.6 Longest period of time seizure free (%)

Longest period of time seizure-free is defined as the percent of the longest seizure free period days divided by the days with available seizure data during double blind phase for Cohort 2 (titration + maintenance), and then multiplied by 100%.

The longest period of time seizure-free will be summarized by treatment group by using descriptive statistics. The 95% confidence interval of the median by treatment group will be presented also.

In addition, a rank analysis of covariance (rank ANCOVA) will be conducted on the longest period of time seizure-free during DB (titration + maintenance), with treatment and pooled center (either US or ROW) as factors and the rank of baseline number of seizure free days per 28-day period as a covariate. The 2-sided significance level of 0.05 will be used for comparison. p-values will be reported. Hodges–Lehmann estimator of the difference in medians together with 95% confidence interval (CI) will be calculated.

8.2.8 Clinical Global Impression of Change

Clinical Global Impression of Improvement (CGI-I): A 7-point Likert scale completed by the Clinician representing the degree to which the subject's epilepsy symptoms have changed relative to baseline. On the CGI-I, 1 = very much improved and 7 = very much worse.

A frequency table will summarize the responses for each treatment by visit, separately for each cohort in each phase. To take into account the ordinal nature of the response, the Row Mean Score Difference, p-value based on Cochran-Mantel-Haenszel test adjusting for pooled center (either US or ROW) will be reported. Clinical Global Impression data will be listed.

8.2.9 Patient/Caregiver Global Impression of Change

[figure not shown]
Patient/Caregiver Global Impression of Improvement (PGI-I): A 7-point Likert scale completed by the Patient or Caregiver representing the degree to which the subject's epilepsy symptoms have changed relative to baseline. On the PGI-I, 1 = very much improved and 7 = very much worse.

A frequency table will summarize the responses for each treatment by visit, separately for each cohort in each phase. To take into account the ordinal nature of the response, the Row Mean Score Difference, p-value based on Cochran-Mantel-Haenszel statistics adjusting for pooled center (either US or ROW), will be reported. Patient Global Impression data will be listed.

8.3 Subgroup analysis

8.3.1 Subgroup Analysis of Subjects Stratified by Inducer/ Non-inducer

Efficacy endpoints of subgroup analysis include:

Inducers are subjects who have taken carbamazepine, phenytoin, oxcarbazepine, primidone or phenobarbital.

Non-inducer subjects are subjects who have not taken any one of the above but may have taken topiramate, levetiracetam, lorazepam, valproic acid, zonisamide, pregabalin, lamotrigine, felbamate, clonazepam, lacosamide or gabapentin. The inducers and non-inducers will be identified from the current AED data.

8.3.2 Subgroup Analysis of Seizure Subtypes

Efficacy endpoints of subgroup analysis include:

- Percent change in 28-day seizure frequency from baseline.
- Change in 28-day seizure frequency.

Descriptive statistics for the efficacy endpoints listed above will be produced for the titration+ maintenance period in the DB phase and the OL phase for both Cohort 1 and Cohort 2 by seizure subtype: CPS, SGTC, SPS-motor and SPS (without motor).

8.3.3 Other Subgroup Analyses

Subgroup analyses on age group (<65, ≥65), gender, ethnicity and geographical region will be conducted also. For each of the subgroups, a separate rank ANCOVA model will be fitted using the same model terms as used for the primary analysis, with additional terms for the subgroup main effect and the treatment by subgroup interaction. The p value to test if the treatment by subgroup interaction is 0 will be presented. Similar output will be displayed for each subgroup as for the primary analysis in Cohort 2. Descriptive summaries only will be displayed for all subgroup analyses in Cohort 1.

Results (Hodge-Lehman estimator and its 95% CI) for all subgroups will be presented in tabular form and forest plots.

9 SAFETY

The population used for safety analyses will be the Safety Population (SP).

9.1 Extent of Exposure

Exposure information will be calculated from the study drug log. Capsule level accountability is not being collected, so exposure to study medication will be summarized as a continuous variable, via the number of days of drug taken. Ganaxolone will be administered BID following the morning and evening meals. Doses should be taken just before or up to 2 hours after a meal or snack, with 240 mL (8 oz.) of water. Each dose should be separated by a minimum of 8 hours and a maximum of 12 hours. A missed dose of study medication may be taken later up to 8 hours before the next scheduled dose; otherwise, the missed dose should not be given.

Exposure data will be summarized using the Safety population for both cohorts.

See tables below for the titration schedules for the transition from DB to OL for both cohorts:

Cohort 1, Phase 2 - Open-Label					
DB Transition to OL					
Visit	Study Day	Dose (mg)/day		Bottle A 225 mg or PBO cap/day	Bottle B 225 mg or PBO cap/day
				GNX: 225mg	GNX: 225mg
		GNX/GNX	PBO/PBO	PBO: 225mg	PBO: PBO
Visit 5	64	1800	900	4	4
	65	1800	900	4	4
	66	1800	1350	6	2
	67	1800	1350	6	2
	68	1800	1350	6	2
	69	1800	1800	8	0
	70	1800	1800	8	0

Cohort 2, Phase 2 - Open-Label					
DB Transition to OL					
Visit	Study Day	Dose (mg)/day		Bottle A 225 mg or PBO cap/day	Bottle B 225 mg or PBO cap/day
				GNX: 225mg	GNX: 225mg
		GNX/GNX	PBO/PBO	PBO: 225mg	PBO: PBO
Visit 5	99	1800	450	2	6
	100	1800	450	2	6
	101	1800	450	2	6
	102	1800	900	4	4
	103	1800	900	4	4
	104	1800	900	4	4
	105	1800	1350	6	2
	106	1800	1350	6	2
	107	1800	1350	6	2
	108	1800	1350	6	2
	109	1800	1800	8	0
	110	1800	1800	8	0
	111	1800	1800	8	0
	112	1800	1800	8	0

These schedules will be used to calculate the exposure for placebo subjects.

Exposure to study medication and cumulative number of days on study medication will be summarized in the DB phase and OL phase for both Cohort 1 and Cohort 2. A summary table of overall exposure to study medication combining the DB phase with OL phase in both Cohort 1

and Cohort 2 will be provided. Ganaxolone group in Cohort 1 will be separated into 2 groups by dose level which are Ganaxolone 1200 mg and Ganaxolone 1800 mg.

A summary table of subjects who reached and maintained maintenance dose of 1800 mg will be provided in each treatment phase for both cohorts. Study drug dosing will be listed.

9.2 Treatment Compliance

A record of all investigational products used will be maintained at each clinical site. This record will include the date the investigational product is dispensed to a subject, initials of the individual dispensing investigational product, quantity dispensed (by unit and strength), the date unused investigational product and empty investigational product containers are returned from the subject, and the quantity returned during Visits 3 through 10 and final post-taper safety assessment. Investigational product and associated accountability forms that are maintained at the clinical site will be present for review by Clinical Research Monitors at each monitoring visit.

At each visit all subjects will receive monthly Subject Seizure Calendars. Each day subjects are to record administration of study drug and background AEDs on the Seizure Calendar.

Compliance with study drug treatment will be assessed by inspecting the Subjects'.

Seizure Calendars and returned supplies with queries as necessary. The Study Drug compliance is a variable in the database calculated using the following formula: $(\text{Stop date} - \text{Start date}) + 1 - \text{number of day's drug not taken} / (\text{Stop date} - \text{Start Date}) + 1$ multiplied 100. This value is calculated for visits 3, 5, 7, 9, 10, 12, 15, and 16. If value is not calculated, a reason should be provided. Per protocol, compliance with background AED medication will be accessed using data from the PK analysis of the AED medication, per SAP [Section 2.1](#) this should be described and issued under a separate analysis plan.

Study treatment compliance will be summarized in DB phase and OL phase for both Cohort 1 and Cohort 2. The ganaxolone group in Cohort 1 will be separated into 2 groups by dose level which are Ganaxolone 1200 mg and Ganaxolone 1800 mg. Study treatment compliance will be listed.

9.3 Adverse Events

The summary of AEs (or SAEs) will be limited to treatment emergent adverse events (TEAEs). A TEAE is any AE (or SAE) occurring on or after administration of the first dose of study medication and before the end of study. An existing AE which worsens on or after administration of the first dose of study medication is also considered a TEAE. AEs will be tabulated by treatment and Overall, system organ class (SOC), and Preferred Term using the MedDRA v.16.0 coding system. The number and percentage of subjects with adverse events will be calculated for each cohort in each phase of the study, by treatment and overall, and in Cohort 1 DB phase, by dose and overall. Additional tables with AEs subset by severity and by relationship to drug as assessed by the investigator will also be presented. Subset listings will be

produced for adverse events that cause withdrawal and for SAEs. Any AE with completely missing start and end dates will be considered a TEAE.

All necessary information about an AE (onset, duration, severity, seriousness, causality to study drug, action taken, and outcome) should be documented by the investigator on the adverse event eCRFs (AE eCRFs). Minimum information required for each AE includes type of event, duration (start and end dates), severity, seriousness, causality to study drug, action taken, and outcome.

Severity of AEs will be graded by the Investigator using the following criteria as guidelines:

1. Mild: Nuisance, barely noticeable.
2. Moderate: Uncomfortable, troublesome symptoms not significantly interfering with daily activities or sleep.
3. Severe: Symptoms significantly interfere with daily activities or sleep.

The relationship of the AE to the study drug should be specified by the Investigator, using the following definitions:

1. Not Related: Concomitant illness, accident or event with no reasonable association with study drug.
2. Unlikely Related: The event has little or no temporal sequence from administration of the study drug, and/or a more likely alternative etiology exists.
3. Possibly Related: The event follows a reasonable temporal sequence from administration of study drug but which could also be explained by concurrent disease or other factors or medications.
4. Probably Related: The event follows a reasonable temporal sequence from administration of study drug, unlikely to be attributed to concurrent disease or other factors or medications. A clinically reasonable response may be observed if the study drug is withdrawn or dose reduced.
5. Definitely Related: The event follows a reasonable temporal sequence from administration of study drug and is definitive pharmacologically; cannot to be attributed to concurrent disease or other factors or medications. A clinically reasonable response should be observed if the study drug is withdrawn or dose reduced.

If discernible at the time of completing an AE eCRF, a specific disease or syndrome rather than individual associated signs and symptoms should be recorded. However, if an observed or reported sign, symptom, or clinically significant laboratory anomaly is not considered by the Investigator to be a component of a specific disease or syndrome, then it should be recorded as a separate AE on the AE eCRF (clinically significant laboratory abnormalities are those that are identified as such by the Investigator and/or those that require intervention).

A Serious Adverse Event (SAE) is any untoward medical occurrence that at any dose (including overdose) that meets 1 or more of the following criteria:

- Is fatal, as a direct outcome of the AE
- Is life threatening

- Requires or prolongs inpatient hospitalization
- Results in permanent or significant disability/incapacity
- Results in a congenital anomaly/birth defect

Any SAEs, including death due to any cause, which occurs to any subject who has signed Informed Consent (personally or by legally authorized representative) in this study or within 30 days following cessation of the last dose of treatment with the study drug, whether or not considered related to the investigational product, must be reported within 24 hours to the Sponsor or their designee. SAEs that occur more than 30 days after the last dose of study drug and are suspected to be related to study treatment should also be reported. All subjects with SAEs must be followed up for outcome.

Adverse events will be summarized by treatment group and overall for each cohort and phase separately for subjects in the Safety Population. In Cohort 1 tables, AE's will be summarized by treatment, dose level, and overall for subjects in the Safety Population, adverse events of subjects pooled in Cohort 1 and Cohort 2 for each treatment phase will be summarized. The following AE tables will be generated:

- An overall summary of the number and percentage of subjects reporting AEs, serious SAEs, treatment-related AEs, AEs leading to treatment discontinuation and AEs leading to death
- AEs overall and by system organ class and preferred term
- AEs by maximum severity, overall and by system organ class and preferred term
- AEs by relationship to study treatment, overall and by system organ class and preferred term
- AEs with onset (or worsening) during titration + 1200 mg/day dose (weeks 1 to 5) and 1800 mg/d (weeks 6 to 9) by preferred term in Cohort 1 DB phase
- AEs with onset (or worsening) during titration phase and maintenance phase by preferred term in Cohort 2 DB phase
- AEs with onset (or worsening) during the de-escalation phase (time interval between Pre-Taper/Early Termination visit and Post-Taper Safety Follow Up visit) by preferred term in Cohort 1 and 2 OL phase

All AEs, SAEs, AEs leading to drug discontinuation and AEs leading to death will be listed.

Missing date will be imputed followed table describes how missing date information will be handled:

Partial Missing Start or Stop Date	Imputed Start Date	Imputed Stop Date
Missing month and day, and the year is present	January 1 of that year or first dose date if the year is the same as the year of first dose date	December 31 of that year
Missing day, but year and month are present	First day of that month or first dose date if the year and month are the same as the year and month of first dose date	Last day of that month
Missing month, but year and day are present	Missing month imputed as January	Missing month imputed as December

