9.4.5 Study Dosing and Dosage Adjustments

Double-blind Phase:

Cohort 1: The study drug dose will be titrated from 400 mg/day to 1200 mg/day in divided doses BID by the end of Week 1 and maintained to Week 5. Dosage will be increased to 1800 mg/day Week 6 and maintained through Week 9 (Table 1).

Cohort 2: The study drug dose will be titrated from 450 mg/day to 1800 mg/day in divided doses BID by the end of Week 2 and maintained through Week 14 (Table 2).

Both titration schedules are consistent with acceptable starting doses and MTDs from previous ganaxolone studies.

Open-Label Phase: Following the completion of the double-blind (DB) phase in either cohort, subjects randomized to placebo will transition to ganaxolone while subjects randomized to ganaxolone will stay on 1800 mg/d. Cohort 1 placebo subjects will begin the 1-week dose titration to 1800 mg/d after completing their Visit 5. Subjects will receive ganaxolone 900 mg/d in divided doses BID for 2 days and step up to 1350 mg for 3 days and then increase to 1800 mg in divided doses BID for 2 days until their Visit 6 (Table 1). Titration for Cohort 2 placebo subjects will mirror the DB phase. Subjects will begin the 2-week dose titration to 1800 mg/d after completing their Visit 5. Subjects will start with 450 mg/d in divided doses BID for 3 days, 900 mg/d in divided doses BID for 3 days, 1350 mg/d in divided doses BID for 4 days, and 1800 mg/d in divided doses BID for 4 days until their Visit 6 (Table 2). At Visit 6, all subjects in both cohorts will be evaluated for tolerability and the investigator will make the determination to maintain the subject on 1800 mg/d or adjust their dose. If the patient experiences any tolerability issues during the transition to OL, such as sedation or dizziness, changes to the titration schedule (e.g., conducting the titration over 3 weeks vs. 2 weeks) may be approved after discussion with the medical monitor. Subjects may be maintained on the MTD of ganaxolone that provides adequate seizure control that is not less than 900 mg/d and not more than 1800 mg/d. Doses may be adjusted upward or downward in 225 mg/d increments every 3 days to reach an optimal dose level over the duration of the 52-week OL phase. Dose adjustments should be made with the investigator's agreement. Frequency of dosing changes may not be less than 3 days unless required for safety.

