9.5.3 Safety Assessments

Planned safety assessments include:

Neurological and physical examinations

Clinical laboratory tests

12-lead ECG

Vital signs including temperature, blood pressure, pulse rate, respiration rate, height, weight and BMI

Columbia Suicide Severity Rating Scale (C-SSRS)

AE monitoring: frequency, severity, duration, causality, outcome

Clinical labs, vitals and ECG measurements may be repeated if needed to corroborate or refute abnormal findings. Both the original and replicate assessments should be recorded in the eCRF.

See [Appendix 1](#) Schedule of Events for timing of Safety Assessments.

Adverse events will be presented for these time periods for Cohorts 1 & 2: ganaxolone vs placebo Titration + Maintenance (Cohort 1: Weeks 1-9, Cohort 2: Weeks 1-14), 1200

mg/d vs placebo (Cohort 1: Weeks 2-5), and 1800 mg/d vs placebo (Cohort 2: Weeks 6-9) for the safety population; open-label (Cohort 1: Weeks 10-61, Cohort 2: 15-66). In addition, tolerability of ganaxolone during the up-titration phases of the study will be compared between the two cohorts. AEs with onset during the titration phase in Cohort 2 will be compared to AEs with onset during the weeks 1-5 in Cohort 1 (1 week titration + 4 week treatment with 1200 mg/day). In addition, in Cohort 2, AEs with onset during the titration phase will be compared to AEs with onset during the maintenance phase. AEs that emerge during the de-escalation period will be tabulated to investigate whether discontinuation of ganaxolone is associated with withdrawal symptoms. Secondary safety outcome measures include those listed below.

Secondary Safety Parameters for Cohorts 1 & 2	Cohort 1		Cohort 2		Combine Cohorts 1 & 2	
	DB Phase	OL Phase	DB Phase	OL Phase	DB Phase	OL Phase
Number of subjects at each dose	X	X	X	X		X
The frequency and proportion of subjects with AEs	X	X	X	X		X
Severity of AEs	X	X	X	X		X
AEs leading to DC	X	X	X	X		X
Incidence of subjects with early DC	X	X	X	X		X
Change from baseline in vital signs (blood pressure, respiration rate and heart rate), body weight and ECG	X	X	X	X		X
Change in clinical hematology and chemistry parameters	X	X	X	X		X
Assessment of suicidality via the Columbia Suicide Severity Rating Scale (C-SSRS)	X	X	X	X		X

Additional assessments may be conducted as considered appropriate.

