- i) Patient Global Impression of Change – Improvement (PGI-I; Patient/Caregiver) at each assessment visit
- j) Clinical Global Impression of Change – Improvement (CGI-I; Investigator) at each assessment visit

Exploratory endpoint

[REDACTED]

The primary and secondary efficacy outcome measures will be assessed for each of the time periods listed below in Cohort 1 DB phase ([a-e] below) and Cohort 1+ Cohort 2 OL if below:

- a) Ganaxolone Titration + Maintenance 1200 mg/day + Maintenance 1800 mg/day vs Placebo (Cohort 1: Weeks 1-9).
- b) Ganaxolone Maintenance 1200 mg/day + Maintenance 1800 mg/day vs Placebo (Cohort 1: Weeks 2-9).
- c) Ganaxolone Titration + Maintenance 1200 mg/d vs placebo (Cohort 1: Weeks 1-5).
- d) Ganaxolone Maintenance 1800 mg/d vs placebo (Cohort 1: Weeks 6-9).
- e) Ganaxolone maintenance 1200 mg/d vs placebo (Cohort 1: Weeks 2-5).
- f) OL (Cohort 1: Weeks 10-61; Cohort 2: Weeks 16-66).

The responder rates and seizure-free rates between ganaxolone and placebo will be compared using a logistic regression analysis. To take into account the ordinal nature of the response to Clinical Global Impression of Change and Patient Global Impression of Change scales (CGI-I, PGI-I), the Row Mean Score Difference, and the p-value based on Cochran-Mantel-Haenszel test adjusting for pooled center (either US or ROW), will be used to test if there is a treatment effect.

Additional assessments may be conducted as considered appropriate. All secondary efficacy variables will also be summarized using descriptive statistics. The exploratory end-point of [REDACTED] will be summarized descriptively only without formal statistical analysis.

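### Protocol 9.5.3 puts the 1800 mg/d AE window in a cohort that its own dosing schedule contradicts, and SAP 9.3 has no table for the protocol's Weeks 2–5 window at 1200 mg/d

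*SAP*

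**What the plan says.** Protocol 9.5.3 sets the AE windows by dose. After the whole double-blind phase it names two windows, the first of them for 1200 mg/d: "mg/d vs placebo (Cohort 1: Weeks 2-5), and 1800 mg/d vs placebo (Cohort 2: Weeks 6-9) for the safety population". The same section separately asks that Cohort 2 titration-onset events be compared with "AEs with onset during the weeks 1-5 in Cohort 1 (1 week titration + 4 week treatment with 1200 mg/day"), and SAP 4.3 repeats that request.

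The dosing text for Cohort 1 in Protocol 9.4.5 reads "The study drug dose will be titrated from 400 mg/day to 1200 mg/day in divided doses BID by the end of Week 1"; its later step is given as "Dosage will be increased to 1800 mg/day Week 6 and maintained through Week 9". For Cohort 2 it reads "The study drug dose will be titrated from 450 mg/day to 1800 mg/day in divided doses BID by the end of Week 2", with that dose held through Week 14. The efficacy list in Protocol 9.7.6 has "Ganaxolone Maintenance 1800 mg/d vs placebo (Cohort 1: Weeks 6-9").

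SAP 9.3 lists one Cohort 1 AE table by onset window: "AEs with onset (or worsening) during titration + 1200 mg/day dose (weeks 1 to 5) and 1800 mg/d (weeks 6 to 9"). It also asks for the Cohort 1 AE tables by treatment and dose level, without saying which weeks make up each dose level. SAP section 10, on changes from the protocol, has a single item, and it concerns the primary efficacy analysis.

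**The concern.** There are two separate problems in the current text. First, a programmer who follows Protocol 9.5.3 literally would tabulate Weeks 6–9 of Cohort 2 for 1800 mg/d, although nothing changes in that cohort's dose in those weeks. Second, a programmer who follows SAP 9.3 would produce no table for the protocol's 1200 mg/d window. The only lower-dose column would include the first week of exposure.

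Protocol 9.1 gives Cohort 1 the purpose of providing tolerability, safety and PK information at 1200 and 1800 mg/d. Readers will look at the two onset columns together. SAP 9.3 reports numbers and percentages of subjects and plans no adjustment for exposure time. One column is longer than the other, and it alone contains treatment initiation.

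**Working it through.** **Windows side by side**

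| Source | Lower-dose window | 1800 mg/d window |
|---|---|---|
| Protocol Table 1 (dosing) | Cohort 1, 1200 mg/d maintenance, days 8–35 | Cohort 1, days 36–63 |
| Protocol 9.5.3, dose versus placebo | Cohort 1, Weeks 2–5 | **Cohort 2**, Weeks 6–9 |
| Protocol 9.5.3 and SAP 4.3, titration comparison | Cohort 1, Weeks 1–5 | none |
| Protocol 9.7.6 and SAP 8.2, efficacy | Cohort 1, Weeks 2–5 and also 1–5 | Cohort 1, Weeks 6–9 |
| SAP 9.3, AE onset table | Cohort 1, **Weeks 1–5 only** | Cohort 1, Weeks 6–9 |
| Protocol 9.7.7 and SAP 9.3, by dose level | no weeks given | no weeks given |

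**Cohort label.** Weeks 6–9 are days 36–63. In Cohort 1 these are exactly the days at 1800 mg/d. In Cohort 2 (Table 2) maintenance runs from day 15 to day 98, which is 84 days, so Weeks 6–9 are 28 of 84 days with the same dose before and after. Only the Cohort 1 reading matches a dose period.

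**Day count from Table 1.**
- Weeks 1–5: 35 days. Days 1–2 are at 400, days 3–4 at 800 and days 5–35 at 1200 mg/d. Mean scheduled dose = (2×400 + 2×800 + 31×1200)/35 = 39,600/35 = 1131 mg/d. Seven days are titration, of which four are below 1200 mg/d.
- Weeks 2–5: 28 days, all at 1200 mg/d.
- Weeks 6–9: 28 days, all at 1800 mg/d.

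The SAP's lower-dose column is therefore 35/28 = 1.25 times as long as its 1800 mg/d column.

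**Possible size.** The documents give no AE hazard by week, so the inputs here are assumptions. Let p be the incidence with onset in Weeks 2–5 and k the ratio of the Week 1 daily hazard to that in Weeks 2–5. With h = −ln(1−p)/28,

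P(35 days) = 1 − exp(−28h − 7kh) = 1 − (1−p)^(1+k/4).

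Example: p = 30%, k = 1 gives 1 − 0.70^1.25 = 36.0%.

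| p (Weeks 2–5) | k = 0 | k = 0.5 | k = 1 | k = 3 |
|---|---|---|---|---|
| 10% | 10.0% | 11.2% | 12.3% | 16.8% |
| 20% | 20.0% | 22.2% | 24.3% | 32.3% |
| 30% | 30.0% | 33.1% | 36.0% | 46.4% |
| 40% | 40.0% | 43.7% | 47.2% | 59.1% |

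The increase over p runs from 0 (k = 0) through 2.3–7.2 points (k = 1) to 6.8–19.1 points (k = 3). With about 46/2 = 23 ganaxolone subjects in Cohort 1, the largest value is 0.191 × 23 = 4.4 subjects.

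**The case against.** The case for leaving the tables alone is fairly strong. Weeks 1–5 is not an SAP invention: Protocol 9.5.3 and SAP 4.3 both require it for the cross-cohort titration comparison, and the SAP 9.3 table fits that purpose. The SAP names the column as titration plus 1200 mg/d, so nothing is hidden. Neither document plans a formal test of 1200 against 1800 mg/d, and where placebo is shown over the same days the length of the window cancels. Dose follows a fixed order, so even equal windows would not isolate it. A Week 1 hazard below the maintenance hazard (k < 1) is also plausible, because Protocol section 7 reports dose-related AEs and days 1–4 are at 400–800 mg/d. The SAP table already uses the right cohort, and no primary or key secondary analysis is touched.

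All of this stands, and it limits the consequence. It does not supply the missing Weeks 2–5 table, give the dose-level tables their weeks, or remove the contradiction over the cohort.

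A reader might also infer two stronger things. One is that the protocol leaves Cohort 1 at 1800 mg/d without any AE table. Protocol 9.7.7 rules that out, since it requires Cohort 1 double-blind AEs by dose level. The other is that eight of Cohort 2's twelve maintenance weeks would go unreported. Protocol 9.5.3 rules that out, since it also presents Cohort 2 Weeks 1–14 and compares titration-onset with maintenance-onset events.

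**Conclusion.** Two inconsistencies hold: the cohort label for 1800 mg/d in Protocol 9.5.3, and the protocol's Weeks 2–5 AE window, which has no counterpart in SAP 9.3 and is not listed in SAP section 10. The undefined dose levels in the other Cohort 1 AE tables are part of the same gap.

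It is tempting to say that the tolerability comparison of the two doses is distorted. The documents do not support that, because they plan no such comparison formally and give no weekly hazards. What they support is that a side-by-side reading of the crude percentages could be biased. The extra week can only add subjects to the lower-dose column, by 0 to about 19 points under the assumptions above. Whether the displayed difference then overstates or understates a dose effect also depends on how AE hazards change with time on treatment, which the fixed order does not allow anyone to separate. The point is worth correcting because it bears on Cohort 1's stated purpose and costs almost nothing. It is no threat to the trial's main conclusions.

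**What to change.** 1. In Protocol 9.5.3, reconcile the cohort label of the 1800 mg/d AE window with Table 1 and the list in 9.7.6, which both give Cohort 1, Weeks 6–9.
2. In SAP 9.3, define the Cohort 1 double-blind AE onset windows once: Week 1 (titration), Weeks 2–5 (1200 mg/d) and Weeks 6–9 (1800 mg/d). Show each for ganaxolone and for placebo over the same weeks. Say so explicitly, because SAP 8.2 sets ganaxolone Weeks 6–9 against placebo Weeks 1–9 for efficacy.
3. Use the two 28-day windows wherever SAP 9.3 calls for Cohort 1 AEs by dose level.
4. Keep Weeks 1–5 as its own column for the cross-cohort titration comparison. It cannot be rebuilt by adding the Week 1 and Weeks 2–5 columns, because one subject can have events in both.
5. List any remaining difference from the protocol in SAP section 10.

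The cost is one more table split and a label correction, with no new data. Week 1 cells will be sparse with about 23 subjects per arm. SAP 9.3 also sets an onset with the day missing in the first-dose month to the first dose date, so such events would all fall in Week 1. They should be flagged there.
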